2.4 Trial Design

This will be a single center trial, in adult critically ill patients. With a cross-over design (Fig. 1), patients will receive in random order on 2 consecutive days 3HHB and placebo.

Patients will receive the investigational product between ICU day 4 and 14, to avoid the time of increase in endogenous ketogenesis that we have previously documented to be present in the first 2 to 3 days in ICU [6]. The investigational product (3HHB) or placebo will be delivered through the enteral feeding tube.

Figure 1: Cross-over design of the trial. In group 1, participants will receive 3HHB on intervention day 1, followed by a placebo on intervention day 2. Group 2 will receive placebo on intervention day 1 and 3HHB on intervention day 2. Repetitive blood sampling is indicated in red.

Patients are typically started on enteral nutrition (EN) within 48 hours of admission, unless they are able to eat. EN is delivered for 2x10h per day (8am-6pm and 8pm-6am), with 2x2h interruption (6-8am and 6-8pm) to measure gastric residual volume (Fig 2). EN is usually started at a low rate, and increased depending on tolerance (as deducted in part from gastric residual volumes). For this trial, the caloric intake will be kept constant over the 2 intervention days avoiding the influence of caloric intake on outcome measures. Patients with nasogastric tubes who are not receiving enteral nutrition are also eligible for inclusion. This will allow to study ketone absorption and clearance in both fed and unfed state in the critically ill patient.

Figure 2: 10 hour feeding scheme. Intermittent administration of 3HHB/placebo (in green) every hour for 6 times.

We will administer 3HHB or placebo via repeated small boluses through the nasogastric feeding tube, as is also done for enterally administered medication. The nasogastric tube will be flushed with a 5% glucose solution prior and after administration of 3HBB or placebo to ensure that the bolus has completely entered the stomach while also avoiding clotting of the nasogastric tube.

The first bolus wil be given at 10 am (after 2 hours of enteral feeding) and this wil be repeated 5 times with one hour interval (6 doses in total). After the last bolus, the patient will be fed for three more hours. The next day, this procedure will be repeated (Fig. 1).

We will first perform this trial with a 25 g dose of 3HHB divided over 6 boluses. The density of 3HHB is 1.07 g/ml, 25 g has a volume of 23.4 ml, so each bolus consist of 3.9 ml 3HHB. Next, we will assess the primary and secondary endpoints in this cohort of patients. If the dose of 25 g is found safe but ineffective for increasing plasma 3-hydroxybutyrate at least with 0.22 mmol/l, a second cohort of patients will be tested with the same cross-over study design but with a higher 3HHB dose (50 g of 3HHB, divided over 6 boluses of 7,8 ml). If this dose is again safe but ineffective, a third cohort of patients will be tested with the same cross-over study design with an increased dose of 75 g of 3HHB, divided over 6 doses of 11.7ml. For each cohort of patients tested (cohort I to test 25 g, cohort 2 to test 50 g and cohort 3 to test 75 g),

16 patients will be included. If a patient is not able to complete the 48h study period (e.g. due to consent withdrawal or due to unplanned surgery or other procedures) and this is not related to safety concerns that are directly attributed to the intervention, an extra patient will be included in order not to compromize the statistical power of the study.

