Title of clinical Trial («Trial»)	A single-centre, placebo-controlled, cross-over randomized controlled trial evaluating the metabolic effects of a ketone ester food supplement in intensive care patients: The KETOCARE RCT		
Protocol Short Title Acronym	The KETOCARE RCT		
Sponsor name	University Hospitals Leuven (UZ Leuven)		
Coordinating Investigator	[name]. [name]		
Contact Address Cl	[name]		
Contact Email Cl	[contact]		
Contact Phone CI	[name]		
Public database nbr	ISRCTN: 13903536		
Sub Investigators	[name]. [name] (UZ Leuven) [name]. [name] (KU Leuven) [name]. [name] (UZ Leuven)		
Medical condition or disease under investigation	Adult critical illness		
Trial rationale	To study the feasibility, safety and tolerability of enteral ketone ester supplementation to increase circulating ketone levels in adult critically ill patients.		
Primary objective	To identify a supplementation dose of enteral ketone esters that is able to increase circulating 3-hydroxybutyrate concentrations in adult crtitically ill patients by at least 0.22 mmol/l.		
Secondary objective(s)	To demonstrate that supplementation of enteral ketone esters is safe.		
Trial Design	Single-center, placebo-controlled, cross-over randomized controlled trial		
	- An increase in plasma 3-hydroxybutyrate by at least 0.22 mmol/l following administration of enteral 3HHB (E)		
	- Plasma levels of 3HHB and metabolites 3-hydroxybutyrate and 1,3- butanediol over time during (6 hour period) and after the intervention (18 hour period) (E)		
Endpoints	- Urine levels of 3HHB and metabolites 3-hydroxybutyrate and 1,3- butanediol over time during (6 hour period) and after the intervention (18 hour period) (E)		
(Efficacy = E;	- Blood glucose concentrations during the 48h-study period (E)		
Safety – S, Tolerability – T)	- Incidence of ketoacidosis during the intervention window and until 18h after stopping study infusion (S		
	- Intolerance for the supplement (including abdominal discomfort or vomiting) (S/T)		
	- Incidence of severe (<40 mg/dl) hypoglycemia during the intervention window and until 18h after stopping study infusion (3HHB or placebo) (S)		
Sample Size	16 patients for each study dose completing the 48h study period (maximum of 48 patients completing the 48h study period in total)		

Dietary supplement, dosage and route of administration	Enteral administration of a ketone ester supplement (3-HHB) in increasing dosage (25g, 50g, 75g)		

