7.1 Sample Size

The study is powered to detect a 0.22 mM within-patient increase in plasma 3HB with 95% certainty, 80% power, calculated with a paired t-test. The anticipated effect size is 0.786 given that patients not treated with ketone esters have a mean difference of 0.001mM between intervention day I and 2 with a SD of 0.28mM (based on prior data from ICU patients) and the anticipated required increase with the administration of ketone esters is 0.22mM (which was the effective increase in the mice studies). If the lower limit of the 95% confidence interval is not above 0.22mM increase, a higher dose will be tested.

Approximately 160 participants will be screened to achieve 16 participants completing the 48h study period or an estimated total of 8 evaluable participants per treatment group.

The screening will be repeated for each dose study. In total a maximum of approximately 480 patients will be screened and a maximum of 3x 16 patients completing the 48h study period will be included.

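### Sixteen completers per dose cannot demonstrate safety as the synopsis sets out to do, and sections 2.4 and 7.1 give escalation rules that differ on safety

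*Protocol*

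**What the plan says.** **Objective.** The only secondary objective in the Trial Synopsis is "To demonstrate that supplementation of enteral ketone esters is safe". The named safety and tolerability endpoints (synopsis and section 2.3) are ketoacidosis, severe hypoglycaemia and intolerance of the supplement.

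**Cohort size.** The synopsis plans "16 patients for each study dose completing the 48h study period", with at most 48 completers. Section 7.1 derives the number from the efficacy comparison only, "with 95% certainty, 80% power, calculated with a paired t-test", and adds "The anticipated effect size is 0.786".

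**Escalation in section 2.4.** After the primary and secondary endpoints of a cohort have been assessed, the step from 25 g to 50 g follows "If the dose of 25 g is found safe but ineffective" in raising plasma 3-hydroxybutyrate by 0.22 mmol/l or more. The step to 75 g repeats the condition: "If this dose is again safe but ineffective, a third cohort of patients will be tested".

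**Escalation in section 7.1.** "If the lower limit of the 95% confidence interval is not above 0.22mM increase, a higher dose will be tested". Safety is not mentioned in that sentence.

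**Stopping in section 4.4.** Intervention-related safety concerns and unacceptable intolerability are among the circumstances that require interruption or discontinuation, and the sponsor or the authorities may halt the trial. The section does not refer to the step between doses.

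**The concern.** There are two separate faults.

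1. To demonstrate safety is a claim about what the data will rule out. A cohort sized for a mean change in a metabolite rules out little about uncommon binary harms. If the objective stands as worded, a cohort with few or no events can be presented as meeting it, although the same data remain compatible with a harm that is common.

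2. The protocol states the escalation decision twice and the statements do not match. Section 2.4 needs two conditions and section 7.1 needs one. This decision determines whether a further cohort receives a higher dose, so the text should allow only one reading.

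**Working it through.** **Step 1: reproduce the plan's sample size.** Inputs from section 7.1: increase 0.22 mM, SD of the within-patient difference 0.28 mM, 95% certainty, 80% power, paired t-test. Sidedness is not stated; two-sided 5% is assumed.

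- Effect size: 0.22 / 0.28 = 0.786, as stated.
- Exact paired t-test power (noncentral t): n = 15 gives 80.8% and n = 16 gives 83.6%.

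The smallest adequate n is 15. The planned 16 covers it and is a multiple of the block size of 4 in section 4.3. The figure is sound for efficacy, and no safety quantity enters it.

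**Step 2: what 16 patients can say about a harm.** Each completer receives 3HHB on one of the two days, so 16 completers are exposed per dose. The most favourable result is no event. That is an assumption made for this check, not a figure in the protocol. With 0 events in n, the exact upper limit solves (1 − p)^n = α/2 (two-sided) or α (one-sided), with α = 0.05.

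| Events | Two-sided 95% upper limit | One-sided 95% upper limit |
|---|---|---|
| 0/16 (one dose) | 1 − 0.025^(1/16) = 20.6% | 1 − 0.05^(1/16) = 17.1% |
| 0/48 (all three doses pooled) | 1 − 0.025^(1/48) = 7.4% | 1 − 0.05^(1/48) = 6.1% |

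The second row applies only if all three cohorts are run, and it mixes three different doses.

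**Step 3: chance of seeing no event in a cohort, (1 − p)^16.**

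- True rate 5%: 0.95^16 = 44.0%
- True rate 10%: 0.90^16 = 18.5%
- True rate 20%: 0.80^16 = 2.8%

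**Step 4: zero-event sample size needed to exclude a 10% rate.**

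- One-sided: ln(0.05) / ln(0.90), rounded up, is 29.
- Two-sided: ln(0.025) / ln(0.90), rounded up, is 36.

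Both exceed 16. The protocol states no acceptable rate; 5%, 10% and 20% are illustrations.

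**Step 5: sensitivity to the denominator.** Patients who stop early may also have been exposed, and some are replaced, so the exposed number can exceed 16. With 0/20 the two-sided limit is 1 − 0.025^(1/20) = 16.8%, which does not alter the conclusion.

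**Step 6: the two escalation statements side by side.** Here ineffective means that the lower 95% limit is not above 0.22 mM.

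| Finding for the current dose | Section 2.4 | Section 7.1, read literally |
|---|---|---|
| Ineffective, safe | Next dose tested | Next dose tested |
| Ineffective, not safe | Condition not met | Next dose tested |
| Effective | Condition not met | Condition not met |

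They differ in one row, where a dose is ineffective and not safe.

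**The case against.** The strongest reply is that section 7.1 is about sample size, and its sentence only gives statistical meaning to ineffective. On that view the operative rule is in section 2.4, which requires safety at both steps, and section 4.4 provides for stopping on safety grounds. This largely stands. A reader might infer from 7.1 that the trial escalates without regard to safety; the documents do not support that, because following 7.1 literally would mean disregarding 2.4 and 4.4. What remains is that 7.1 says, without qualification, that a higher dose will be tested, and nothing there refers back to 2.4.

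On the objective, it can be said that *demonstrate* occurs only in the synopsis objective, that the synopsis rationale speaks of studying safety and that section 2.3 already lists incidences. It can also be said that any cohort of 16 has this limitation, and that the protocol neither equates safe with zero events nor relies on these counts alone: there is a within-patient placebo day, glucose and ketones are measured every 4 hours, and prior use in healthy adults is cited. All of this is fair. It shows that the body of the protocol is closer to estimation than its stated objective. It does not make the objective attainable, and no separate analysis plan could do so at this cohort size.

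Two further inferences should be resisted. Section 7.2 gives no confidence intervals for the safety incidences, but that detail is commonly left to a statistical analysis plan, which is not shown, so it is not a fault of the protocol. Nor is there any need to replace the word safe in 2.4 with a softer phrase, since that would change no decision.

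**Conclusion.** The point holds for two statements. The secondary objective claims more than the design can deliver: in the best case of no events, a true rate of up to 20.6% per dose (two-sided; 17.1% one-sided) is not excluded. The escalation sentences in 2.4 and 7.1 conflict for a dose that is ineffective and not safe.

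The numerical part rests on 16 exposed patients per dose, independent patients, exact binomial limits and the assumed zero count; any observed event would raise the limits. The second part rests on the text alone. Neither affects the primary efficacy estimate or the sample size. They bear on how safety results may be described and on how the dose-step decision is read.

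**What to change.** 1. In the Trial Synopsis, restate the secondary objective as estimating the incidence of the named safety events (ketoacidosis, severe hypoglycaemia, intolerance) at each tested dose. Few or no events would then be reported with their exact 95% limits and not as proof of safety. The observation window for ketoacidosis and hypoglycaemia should be settled in the same edit, since the synopsis runs it to 18 h after stopping the infusion and section 2.3 to 12 h.
2. Reconcile the escalation sentences in sections 2.4 and 7.1 so that both carry the same condition, for instance by stating the rule once and cross-referring to it. What counts as safe, and what follows if a dose is not, is for the sponsor to decide; nothing is proposed here.

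The cost is a few sentences in a protocol amendment, with no extra patients, visits or assays. The price is a more modest safety statement.

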2.5 Translational research

Blood glucose and 3-hydroxybutyrate concentrations will be quantified repeatedly using blood gas analysis and point-of-care devices during the 48h trial window.

For this trial, we will collect blood samples at 10 ± 1 am on ICU test day I, before administration of the first bolus, repeat this every hour, up to I hour after the last bolus (4 pm), and then every 2 hours until 12h post final bolus (4 am on ICU test day 2). We will repeat this on test day 2. In total, 26 samples (104 ml blood) will be collected from each patient. To minimize blood waste and reduce infection, we will use a VAMP system for blood sampling. Each sample consists of I EDTA tube (purple K2E tube - BD Vactutainer 368861) containing 4 ml of blood. Samples will be stored on ice immediately and processed for further analysis. After processing, samples will be frozen at -20°C and stored at -80°C.

We will collect a urine sample from the 24h urine collection at 8 am ± 1 hours at the end of both intervention days. These samples will be processed, frozen and stored at -80°C for further analysis.

As a standard of care, whole blood glucose measurements are performed every 4 hours on arterial blood using a blood gas analyzer in the ICU. Using the left-over of this clinically collected sample, we will also measure 3-hydroxybutyrate using ketone test strips (Nova StatStrip).

2.6 Expected Duration of the Trial

Patients will receive 3HHB or placebo, which will be administered over 6 hours on two consecutive days in ICU (between ICU day 4 and day 14). Repeated measurements will be done on blood and urine during the 48h intervention. The last sample will be taken on the morning following the 2nd intervention day in the ICU. This is the end of the intervention for the individual patient. We will do a clinical follow-up for at least 48 hours after the intervention.

Since we will only include patients who have an expected ICU stay of at least 5 days, we estimate that we will need a 2-4 month screening period. This can be doubled or tripled when we need to test higher doses of ketones.

3 Trial Population / Eligibility Criteria

3.1 Inclusion criteria

Participants eligible for inclusion in this Trial must meet all of the following criteria:

- Voluntary written informed consent of the participant or their legally authorized representative has been obtained
- Age >= 18 years
- Patient expected to stay at the ICU for at least 5 days
- The presence of a nasogastric feeding tube

All participants who are considered for Trial participation, per the above criteria will be documented on the Screening Log, including Screen Failures.

3.2 Exclusion criteria

Participants eligible for this Trial must **not** meet any of the following criteria:

- Therapy restriction code
- Patients refusing blood transfusion upon ICU admission will be considered as having a therapy restriction upon admission and will not be included
- Expected to die within 48 hours after screening (= moribund patients)
- No arterial and central venous line, or expected to have one of these lines removed before the end of the study period (= not critically ill enough to be representative for the future target population).
- Contraindication for enteral feeding
- Readmission to the ICU after previous inclusion in the RCT
- Inborn metabolic disease
- Receiving ketogenic diet in ICU
- Underweigt (BMI<20) or admitted with complications due to anorexia nervosa
- Known to be pregnant or lactating
- ICU admission with diabetic ketoacidosis or hyperosmolar hyperglycemic state
- Acute or chronic liver failure
- High glucose need to prevent spontaneous hypoglycemia
- Metabolic acidosis (pH <7.30 and bicarbonate <18mmol/l)
- Patient receives Extracorporeal membrane oxygenation (ECMO)

Participants who meet one or more of the above exclusion criteria must not proceed to be enrolled/randomized in the Trial and will be identified on the Screening Log as Screen Failure.

4 Trial Procedures

4.1 Participant consent and withdrawal of consent

The Trial will be conducted only on the basis of prior informed consent by the Trial participants and/or their legally authorized representative(s). As such, no Trial-related procedures will be conducted prior to obtaining written informed consent from potential Trial participants.

In the majority of patients, we expect that informed consent will have to be obtained from the patient's closest family member or legal representative due to the nature of their illness. As regaining consciousness and mental competence often occurs gradually and slowly in these patients, it is very difficult to determine at what time the patient is able to give a valid informed consent. In addition, recovery can take from several days to several months. Often, patients are only able to give a valid consent after discharge from ICU, at what time the intervention is already terminated. Therefore, we will give an opting out form to the legal representative, who can give it to the patient once he/she is well recovered. With this document, the patient has the possibility to terminate the study intervention (if still applicable) and/or withdraw from further data collection.

The process for obtaining and documenting initial and continued informed consent from potential Trial participants will be conducted in accordance with ICH-GCP E6(R2), applicable regulatory requirements and internal Standard Operating Procedures (SOPs).

All originally signed obtained Informed Consent Forms (ICFs) must be retained/archived in the Trial Master File (TMF) and must not be destroyed (even when a scanned copy is available) before expiration of the legal archiving term as defined in the protocol section entitled "Archiving".

Participants may voluntarily withdraw consent to participate in the Trial for any reason at any time. The participant's request to withdraw from the Trial must always be respected without prejudice or

consequence to further treatment. Consent withdrawal will be documented in the participant's medical record.

Trial data collected before withdrawal can be used in the trial. Results of analyses on samples obtained before withdrawal of consent can also be used. No new trial data or samples will be collected after withdrawal of the participant. No new analysis on samples will be performed after withdrawal.

4.2 Selection of Participants / Recruitment

Patients will be included in the study if they meet all inclusion criteria that are described above (Subparagraph 3.1 – Inclusion criteria). Screening for inclusion will be done on working days, and exceptionally, during the weekends or legal holidays depending on the research staff availability. Screening for inclusion will be performed by the principal investigator or delegate members of the research team.

4.3 Randomization Procedure

A blocked randomization scheme with blocks of 4 patients will be used in this study. The code for randomization blinding is stored in the randomization tool, developed in FilemakerPro with restricted access to the database administrators. Randomization will be carried out by dedicated research staff members using a role-based user access.

4.4 Premature discontinuation of Trial treatment

Participants may voluntarily discontinue from Trial treatment and/or prematurely end their participation in the Trial for any reason at any time. In such case the Investigator will make a reasonable effort to document the primary reason for this decision.

The Investigator may also decide at any time during the course of the Trial, to temporarily interrupt or permanently discontinue the Trial intervention if it is deemed that continuation would be detrimental to, or not in the best interest of the participant.

Similarly, the Sponsor, CA/EC can decide to halt or prematurely terminate the Trial when new information becomes available whereby the rights, safety and well-being of Trial participants can no longer be assured, when de integrity of the Trial has been compromised, or when the scientific value of the Trial becomes obsolete and/or unjustifiable.

Circumstances requiring premature treatment interruption or discontinuation of the Trial, include but are not limited to:

- Safety concerns that are directly related to the intervention or unacceptable intolerability
- Trial participation while in violation of the inclusion and/or exclusion criteria
- Pregnancy

In any such case of early Trial termination and/or treatment interruption/discontinuation, the Investigator will continue to closely monitor the participant's condition and ensure adequate medical care and follow-up.

5 Trial product of interest

Food supplement (& company brand name)	Used within Indication? (Y or N)	Route of administration (po,sc,iv,)	Dose/dosage and units
deltaG Ketone	Not applicable	Enteral (gastric tube)	25g / 50g / 75g

DeltaG Ketones are commercially available as a soluble food supplement (called 'deltaG Ketone Performance'). We will be using pure deltaG Ketone ester as ketone supplement (100% R-3-hydroxybutyl-R-3-hydroxybutanoate, $C_8H_{16}O_4$). This ketone product has been developed at the university of Oxford and was shown to be safe and efficacious in healthy human volunteers [17]. Since 2008, deltaG has been the subject of a wide range of scientific safety studies that led to a Generally Recognized as Safe (GRAS) designation and a U.S. FDA notification. This supplement is also currently being investigated in patients with type I diabetes [18], in patients with type 2 diabetes and heart failure [19] and in a KU Leuven trial with athletes [20]. The food supplement will be delivered to us by deltaG.

As described in chapter 2.4 (Trial design), 3HHB and placebo will be administered through the same feeding tube as EN. A syringe with the intervention product will be attached to the tube port and instilled by slowly and steadily pushing on the plunger. A flush of 10 ml 5% glucose will be given after each administration to prevent clotting of the tube. After the last (6th) bolus administration, we will flush with 50 ml 5% glucose. We will also use 5% glucose as placebo.

6 Safety reporting

